#### Optional Qualitative Follow-Up

An optional qualitative follow-up survey will be offered to participants who complete at least 1 activity in the Happify for Teens application, complete the follow-up assessment and at least one of the following: Midpoint or Post Assessment. This survey will include 13 open-ended questions, 2 close-ended questions, and 3 fill in the blank questions. The survey questions will focus on 3 topics: overall perceptions and preferences of Happify, perceived impacts of the app for improving mental health, and overall usability, acceptability and likability of Happify for Teens.

The survey is estimated to take 40 minutes to complete per participant. See Appendix K for details describing this follow-up

#### c. Study Conditions:

- i. **Happify:** Participants assigned to the experimental condition will be sent a link to download the Happify Teens platform, as well as instructions on how to get started. These participants will have full access to the Happify for Teens platform for the entire 12-week study period. Happify for Teens has multiple tracks that target specific issues (e.g., “The Friendship Project”), which contain activity variants and games based on research in positive psychology, cognitive-behavioral therapy, mindfulness, etc.. Track activities are organized into five categories based on the acronym STAGER: savor (savoring and mindfulness), thank

(gratitude), aspire (goal-setting, reframing/optimism, and meaning), give (prosocial behavior, kindness, and forgiveness), empathize (perspective-taking and self-compassion), and revive (physical health). Although participants have access to all tracks on the Teens platform, four tracks related to stress and rumination will be featured: *Stress Buster 101, Stop the Worry Cycle, Be Kinder to Yourself, and Fight Those Negative Thoughts*. Participants will also have access to instant play activities. An example of an activity on Happify is called “Today’s grateful moment”, which asks participants to spend a few moments writing about something they are grateful for. They will not be told directly how often to engage with the platform; however, we will encourage them to engage with the platform regularly. Participants also will receive push notifications on their mobile device every other day to remind them to access the platform, and they will receive weekly emails as part of the Happify Health platform to help increase engagement. If a participant has not completed any activities within the platform for 7 days, they will also receive a text message or email (depending on their preferred mode of contact) from a member of the research team to check in. Participants will continue to have access to the Happify for Teens platform for an additional 4 weeks after the intervention period ends (until the 12-week assessment), but will receive no instructions, reminders or push notifications to use the platform during this time.

**ii. Waitlist comparison:** Participants assigned to this condition will be notified that they have been assigned to the waitlist control condition and will receive access to the Happify for Teens platform after the 12 week study period. They will be asked to refrain from downloading Happify in this time period and that they will still need to complete assessments in 4 weeks, 8 weeks, and 12 weeks time as part of the study.

**d. Study Duration:** It is expected that this study will take 12 weeks to complete. Users will be asked to complete a baseline questionnaire after assenting to participate in the study, and based on completion, will then be assigned to either the Happify condition or the waitlist control condition. Participants will be asked to complete a mid-point assessment at 4 weeks, a post-test questionnaire at the end of the 8-week intervention period and one month after the post-assessment, users will be asked to complete a follow-up questionnaire. They will receive check-ins via their preferred method of contact every 2 weeks throughout the study that ask if they have any questions and thank them for their participation. Participants and parents of participants will also receive thank you messages at the end of the study.

#### **e. Design and Proposed Statistical Analysis**

**I. Changes in Stress and Secondary/Exploratory Outcomes:** To assess whether changes in participants' perceived stress differed across the two groups, we plan to conduct a 2 (group: intervention vs. control) x 4 (time: baseline, 4 weeks, 8 weeks, 12 weeks) repeated-measures ANOVA on participants' PSS scores, controlling for participant age and gender. Similar analyses will be conducted on secondary and exploratory outcome measures. To determine whether usage predicted changes in these outcomes, we will also conduct regression analyses among participants in the intervention condition regressing their scores on each outcome variable onto the number of activities completed within the Happify for Teens platform, while controlling for corresponding baseline scores on that outcome.

ii. **Rumination as a Potential Mediator:** To test whether any observed changes in perceived stress can be attributed to changes in brooding, we also plan to conduct mediation analyses using Hayes' PROCESS macro for SPSS.

iii. **Data Exclusion:** Because careless responding is problematic with online surveys and may artificially increase relationships between variables, we plan to use two separate a priori mechanisms for identifying low quality data: (1) failing 3 or more attention checks in an assessment, and (2) completing an assessment at a rate faster than 1 second per item. We will then re-run the analyses described above without these participants to test whether effects differ when removing low quality data.

iv. **Happify Scale Validation:** To validate the scale for internal purposes, we will conduct confirmatory factor analysis testing the two-factor structure of the scale, and examine convergent validity by computing correlations between the positive emotion subscale and the PANAS-C-S and between the life satisfaction subscale and the SLSS that are collected at baseline.

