- ii. The Qualtrics prescreener link will then be sent to the child. It includes verifying their country of residence, age, and previous Happify use. They will also complete the Perceived Stress Scale (PSS) and Ruminative Responses Scale (RRS) to ensure their scores are above thresholds (PSS  $\geq$  10; RRS  $\geq$  14). Finally, the participant must agree to study duties, including: completing the baseline assessment, completing activities via Happify through a computer or smartphone, and being contacted throughout the 12 week period by Happify research staff. Participants are told that they may be assigned to a waitlist control and will not have access to the Happify platform until the end of the study but will still have to complete assessments. They are asked to check a box if they would be willing to continue with the study and not download Happify if assigned to the waitlist. We will ask participants to agree to not discuss the study with friends or family also participating in the study. If the child meets the inclusion criteria, they will be instructed that they'll receive an email inviting them to complete the first assessment (baseline assessment) on the following Monday or Thursday (whichever comes first). They must complete this assessment in order to qualify for the study, and must continue to meet thresholds for perceived stress and rumination, and pass at least one of 7 attention checks during the baseline assessment. This email will have instructions to set up a unique study ID that will be used throughout the study to link participant data across assessments and other data collections.
- iii. In this email, participants will be provided an assent form (through Qualtrics) which is shown at the beginning of the baseline assessment. If participants choose to, they will read and agree to a statement that they will provide honest and thoughtful responses throughout the study, and a separate statement agreeing not to discuss the study with any family or friends who may also be participating in the study. Participants must complete the baseline to be randomized to condition. Participants are

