required to pass at least one of the attention checks in the baseline assessment. These attention checks require people to select a specific response option (e.g., for the PSS, an attention check item could instruct the participant to select “Never”, and this would vary across all assessments). Participants who complete and pass the baseline assessment on Qualtrics will be randomly assigned, via a Qualtrics randomization tool, to either the experimental or waitlist control group, and will receive an email or text (through Simple Text) with information detailing their condition on their corresponding start date. If they are in the experimental condition, they will also receive a link to download Happify. Both groups will complete assessments at 4 (mid-point), 8 (immediate post-intervention), and 12 weeks (one month post-intervention) via their preferred method of contact which was obtained in the baseline (e.g. email or text). All participants will be prompted to provide their user ID and complete the PSS, RRS - Brooding Subscale, LOT-R, PROMIS Pediatric Sleep Disturbance scale, and the RULS-8 via Qualtrics at each assessment point. Participants will also be asked at each assessment point if they have sought out help from other online platforms and what their current schooling situation is (fully remote, hybrid model, fully in person, home-schooled, or not in school). All of the assessments will have one attention check per questionnaire, which will instruct participants to select a specific response option to ensure they are reading questionnaire items and instructions carefully. The SLSS and PANAS-C-S will be administered only during baseline for scale validation purposes, and the experimental group will receive the Happify scale as part of the app experience every 2 weeks. In both cases, participants who do not qualify for the study will be thanked and alerted through Qualtrics that they do not qualify, and all their survey information will be deleted to protect their confidentiality. Participants who do not complete the baseline assessment will not go onto the study and will also have all of their information deleted.

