**b. Study Measures:**

- i. Usage statistics such as number of activities completed and number of active days will be collected.
- ii. Major assessments will consist of several validated and published scales that assess aspects of participants’ mental health, and information about the participant. All scales also have been used in previous peer-reviewed research with adolescents. Scales are listed below, and the full text of all scale items can be found at the end of this document.
  1. Perceived Stress Scale (PSS; Cohen, Kamarck & Mermelstein, 1983): 10-item measure of perceived stress

2. Ruminative Responses Scale (RRS) - Short Form - Brooding Subscale (Treynor, Gonzalez, & Nolen-Hoeksema, 2003): 5 items which measure moody pondering over 7 days
3. Life Orientation Test-Revised (LOT-R; Scheier & Carver, 1985), 10-item measure on optimism
4. Roberts UCLA Loneliness Scale (Roberts, Lewinsohn, & Seeley, 1993): 8-item measure of subjective feelings of loneliness and social isolation
5. PROMIS Pediatric Sleep Disturbance Scale - Short Form 4a (Yu et al., 2012): 4-item scale measuring the frequency of sleep disturbances over 7 days

iii. Other Outcomes

1. Happify Scale (proprietary scale, developed by [name]): 9-item measure of cognitive and emotional well-being. This scale is given every 2 weeks, as part of the Happify platform experience.
2. Student Life Satisfaction Scale (SLSS; Huebner, 1991): measures life satisfaction in school-aged children and adolescents; is only given during the baseline assessment in order to validate the Happify Scale with adolescents.
3. Shortened Positive and Negative Affect Schedule for Children (PANAS-C-S; Ebetsutani et al., 2012), which measures positive and negative emotions in youth; is only given during the baseline assessment for validation purposes.
4. Demographic Questions (baseline assessment only):
  - a. Race and Ethnicity Question: “What is your race or origin?” (check all that apply). Participants will select from, “American Indian or Alaska Native”, “Asian”, “Black or African American”, “Hispanic or Latinx”, “Native Hawaiian or Other Pacific Islander”, “White”, or “Some other race or origin”. Then participants will be asked if they identify with a race or origin that was not on the list, and if they select “yes”, participants will be asked to “Please specify”, and they will be given a text box to type in.

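### The Happify Scale and the two measures meant to validate it are never given in the same survey, so the planned correlations are lagged and come from one arm only (minor; cheap to correct)

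*Protocol*

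**What the plan says.** Protocol II.e (Happify Scale Validation) sets out two analyses for internal use: a confirmatory factor analysis of the scale's two-factor structure, and a check to "examine convergent validity by computing correlations between the positive emotion subscale and the PANAS-C-S", paired with a correlation between the life satisfaction subscale and the SLSS. It does not say which Happify Scale administration supplies the scores.

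The timing is given in II.a and II.b:

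- Criterion measures: "The SLSS and PANAS-C-S will be administered only during baseline for scale validation purposes". II.b repeats that the SLSS "is only given during the baseline assessment in order to validate the Happify Scale with adolescents".
- Happify Scale: "the experimental group will receive the Happify scale as part of the app experience every 2 weeks", and in the measures list, "This scale is given every 2 weeks, as part of the Happify platform experience".
- Scales for everyone at every assessment: participants are to "complete the PSS, RRS - Brooding Subscale, LOT-R, PROMIS Pediatric Sleep Disturbance scale, and the RULS-8 via Qualtrics at each assessment point". The Happify Scale is not among these five.

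The app link is sent after baseline and randomisation, to the experimental arm (II.a). The waitlist arm gets the app after week 12 (II.c), and anyone who has already used Happify is excluded (III.c). The SAP does not mention the validation analysis.

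**The concern.** Convergent validity is normally read from two instruments completed together. Here the criterion is measured before randomisation and the scale under test is measured later, in one arm, by those who open the app. The resulting coefficient combines three things: how well the two instruments agree, how stable the construct is over the gap, and how far users differ in their response to the app. A low value could not be assigned to any one of them.

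The only stated purpose of the SLSS and PANAS-C-S is this validation. About 400 waitlist participants complete both, and under the written schedule their answers cannot enter either correlation. Because the app gives the scale repeatedly and the plan names no administration, the choice could also be made after the results are known.

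**Working it through.** **1. Is the Happify Scale in the baseline survey?** The protocol's own count gives an independent check. II.a states "All of the assessments will have one attention check per questionnaire" and requires participants to "pass at least one of 7 attention checks during the baseline assessment".

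- Recurring scales: PSS, RRS-Brooding, LOT-R, PROMIS Sleep Disturbance, RULS-8 = 5
- Baseline-only scales: SLSS, PANAS-C-S = 2
- Total: 5 + 2 = 7, which reproduces the stated 7. With the Happify Scale it would be 8.

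The count fits a baseline without the Happify Scale. Exclusion of earlier users rules out a score from before baseline.

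**2. Pairs available** (III, Sample Size: 800 in total, 400 per condition).

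- Same-survey pairs: 0
- Lagged pairs: at most 400 of 800, all experimental arm, fewer if some never open the app
- Waitlist participants with criterion scores but no Happify Scale score in the study period: about 400

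**3. Expected size of the correlation.** The documents give no expected correlation, stability or lag, so these are assumptions:

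- same-time correlation 0.60
- stability of the underlying construct between baseline and in-app completion, among treated users, 0.6 to 0.9. This covers both natural drift and differing response to the app.

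Formula: expected r = same-time r × construct stability. The 95% interval uses Fisher's z: tanh(atanh(r) ± 1.96/√(n − 3)), with n = 400 as the upper limit.

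| Construct stability | Expected r | 95% interval, n = 400 |
|---|---|---|
| 1.0 (no effective gap) | 0.60 | 0.53 to 0.66 |
| 0.9 | 0.60 × 0.9 = 0.54 | 0.47 to 0.61 |
| 0.8 | 0.60 × 0.8 = 0.48 | 0.40 to 0.55 |
| 0.7 | 0.60 × 0.7 = 0.42 | 0.34 to 0.50 |
| 0.6 | 0.60 × 0.6 = 0.36 | 0.27 to 0.44 |

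For comparison, a same-time baseline measure in all 800 would give 0.60 with an interval of 0.55 to 0.64. At stability 0.9 the lagged interval still contains 0.60. At 0.8 or below it does not, so the shortfall is then more than sampling error.

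**4. Which stability applies.** The multiplier must be stability of the construct, not the observed test-retest correlation. Measurement error is already in the 0.60, and the observed figure would count it again. As an illustration with an assumed reliability of 0.85, an observed stability of 0.70 corresponds to 0.70/0.85 ≈ 0.82 for the construct, and 0.60 × 0.82 ≈ 0.49 rather than 0.42.

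**The case against.** A reader might infer that the validation aim cannot be met at all. The documents do not support that:

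- The factor analysis needs no criterion measure and remains possible, though only in treated users.
- The first in-app completion is not dated. If it comes at first login, the gap may be days with almost no exposure, and the correlation would be close to its same-time value.

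A reader might also infer that any benefit from the app distorts the result. It does not: a uniform improvement moves the mean and leaves a Pearson correlation unchanged. Only differences between users in their response matter.

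The magnitude rests entirely on assumed inputs, so no single figure in the table should be quoted as the expected result. The validation is for internal use and is not among the SAP objectives (Section 3), which limits its importance.

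All of this stands, and it reduces the point to a minor one. It does not remove it: at any lag, the pairs are not from one survey, the sample is one arm's app users, and the plan leaves the administration open while calling the result convergent validity.

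**Conclusion.** The mismatch follows from the written schedule, and the attention-check count agrees with it. The two correlations would rest on no same-survey pairs and at most about 400 lagged ones, all treated. Under the assumptions above, 0.60 would be expected to fall to between 0.36 and 0.54, with little loss if the scale appears at first login. The documents cannot settle where in that span the trial lies. What they support is a coefficient that cannot be cleanly interpreted as convergent validity, not a failed validation. No primary, secondary or exploratory treatment comparison depends on it. Minor.

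**What to change.** **At the design stage:** add the 9-item Happify Scale to the baseline Qualtrics survey for all participants, and run the factor analysis and both correlations on those data. This gives up to 800 same-survey pairs before randomisation. The costs are a slightly longer survey, validation of a survey version rather than the in-app version, and an update to the count of seven attention checks in II.a and III.c.

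**Now:** SAP Section 2 reports that assessment data were pulled in March/April 2022, so baseline can no longer be changed. State in the plan that:

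- only the first in-app completion is used
- its lag from baseline and the number of participants contributing are reported
- the sample, for the factor analysis as well, is treated app users only
- the result is called a lagged correlation, not convergent validity.

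This changes wording and reporting only and needs no new data.

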### III. RECRUITMENT

a. **Study Population:** This study will recruit adolescents aged 13-17 (Target  $N=800$ ) by advertising to parents on social media (e.g. Facebook, online forums, word of mouth etc...) and existing Happify users who have previously indicated they are parents of adolescents as part of the Happify onboarding process. We will also use a snowballing recruitment method, in which parents who complete the prescreener will be encouraged to share the study with others. We will continue recruiting until 800 participants have met inclusion criteria, successfully completed the baseline assessment, and have started the study.

b. **Inclusion Criteria:** Participants are those who are 13-17 years old, are located in the United States, are a new user of Happify, willing and able to complete the study activities, agree to potentially being selected for the waitlist comparison, agree to not discuss the study with friends or family, report elevated levels of perceived stress (PSS score of at least 14) and rumination (RRS-Brooding score of at least 10), and have a

parent who is willing to consent to the study. Participants are required to complete and pass the baseline assessment to be included in this study.

**c. Exclusion Criteria:** Participants may withdraw from the study or skip assessments at any time; however during the prescreening and/or baseline process, potential participants will be disqualified if they indicate:

- i. They are not 13-17 years old.
- ii. They reside outside of the United States
- iii. They have previously registered for or used Happify
- iv. They are not willing and able to complete the study activities
- v. They indicate that they are not willing to continue the study or refrain from downloading Happify if selected to be on the waitlist
- vi. They are not willing to use a mobile app or internet website
- vii. They do not agree to refraining from discussing the study with friends or family
- viii. They have a PSS score of below 14
- ix. They have an RRS-Brooding score of less than 10
- x. They do not agree to be contacted
- xi. Their parent does not consent to the study
- xii. Participants will also be excluded if they do not complete the baseline assessment, or if they do but fail at least 7/7 attention checks.

2. **Sample Size:** We will recruit 800 participants to be in this study, 400 in each condition.
3. **Withdrawal:** Participants may choose to withdraw from the study at any time. Data that has been collected up until that point will be available to the research team for analysis. Participants can withdraw by contacting the research team, and then they will be promptly removed from the study.

#### **IV. CONSENT PROCESS**

**a. Consent Process:** Parents who are interested in having their adolescent children participate must read about the study procedures and requirements, and actively check a box that indicates they understand the requirements of the study. To consent, they will draw their signature on an online form through Qualtrics. They will draw a signature and check a box for each child. Adolescents who would like to participate read about the procedures and requirements of the study, and actively check a box that indicates that they understand the requirements of the study before they begin the baseline assessment. To assent, they click a box that says, “YES, I would like to participate in this study.” Consent and assent will be obtained for all participants before enrolling them in the study and beginning the baseline assessment.

**b. Consent Documentation:** Electronic records of participant assent and parental consent will be downloaded through Qualtrics and moved to Happify servers, where they will be maintained.

